### 8.2.1 Physical Examinations

- A complete physical examination will include, at a minimum, assessments of general appearance, skin, head, neck (including thyroid), eyes, ears, nose, throat, abdomen, as well as neurological, peripheral vascular, musculoskeletal, cardiovascular and pulmonary system.
- Height (at Screen) and weight will also be measured and recorded.
- A brief physical examination will include, at a minimum, assessments of the skin, lungs, cardiovascular system, and abdomen (liver and spleen).
- Investigators should pay special attention to clinical signs related to previous serious illnesses.

### 8.2.2 Vital Signs

- Tympanic temperature, pulse rate, and blood pressure will be assessed.

- Blood pressure and pulse measurements will be assessed semisupine with a completely automated device. Manual techniques will be used only if an automated device is not available.
- Blood pressure and pulse measurements should be preceded by at least 5 minutes of rest for the participant in a quiet setting without distractions (e.g., television, cell phones).

### 8.2.3 Electrocardiograms

- Single 12-lead ECG will be obtained as outlined in the SoA using an ECG machine that automatically calculates the heart rate and measures PR, QRS, QT, and QTc intervals.

### 8.2.4 Clinical Safety Laboratory Assessments

- Blood and urine samples will be collected for the clinical laboratory tests listed in [Appendix 5](#) at the time points listed in the SoA. All samples should be clearly identified.
- Additional tests may be performed at any time during the study, as determined necessary by the Investigator or required by local regulations.
- The tests will be performed by the Nuvisan laboratory. Reference ranges of the laboratory parameters for the Nuvisan laboratory are provided in [Appendix 8](#).
- The Sponsor must receive a list of the local laboratory normal ranges before shipment of study intervention(s). Any changes to the ranges during the study must be forwarded to Sponsor.
- The Investigator must review each laboratory report, document this review, and record any clinically relevant changes occurring during the study in the AE section of the CRF. The laboratory reports must be filed with the source documents.
- A Laboratory Manual will be prepared which contains the following information: sampling methods (e.g. whole blood, plasma, serum, urine), processing and storage of samples through to the analysis, and any special analysis methods.

### 8.2.5 Suicidal Risk Monitoring

Not applicable.

## 8.3 Adverse Events and Serious Adverse Events

The definitions of an Adverse Event (AE) and a Serious Adverse Event (SAE) are in [Appendix 4](#).

### 8.3.1 Time Period and Frequency for Collecting Adverse Event and Serious Adverse Event Information

The AE reporting period for safety surveillance begins when the participant is initially included in the study (date of first signature of informed consent/date of first signature of first informed consent) and continues until the end of the Safety Follow-up.

Any SAE assessed as related to study intervention must be recorded and reported, as indicated in [Appendix 4](#), whenever it occurs, irrespective of the time elapsed since the last administration of study intervention.

The method of recording, evaluating, and assessing causality of AEs (including SAEs) and the procedures for completing and transmitting SAE reports are in [Appendix 4](#).

### **8.3.2 Method of Detecting Adverse Events and Serious Adverse Events**

At each study visit, the participant will be queried on changes in his or her condition. During the reporting period, any unfavorable changes in the participant's condition will be recorded as AEs, regardless if reported by the participant or observed by the Investigator.

Complete, accurate and consistent data on all AEs experienced for the duration of the reporting period (defined below) will be reported on an ongoing basis in the appropriate section of the CRF. All SAEs must be additionally documented and reported using the appropriate Report Form as specified in [Appendix 4](#).

### **8.3.3 Follow-up of Adverse Events and Serious Adverse Events**

AEs are recorded and assessed continuously throughout the study, as specified in [Section 8.3.1](#) and are assessed for their outcome at the Safety Follow-up Visit. All SAEs ongoing at the Safety Follow-up Visit must be monitored and followed up by the Investigator until stabilization or until the outcome is known, unless the participant is documented as "lost to follow-up". Reasonable attempts to obtain this information must be made and documented. It is also the responsibility of the Investigator to ensure that any necessary additional therapeutic measures and follow-up procedures are performed. Further information on follow-up procedures is given in [Appendix 4](#).

### **8.3.4 Regulatory Reporting Requirements for Serious Adverse Events**

The Sponsor will send appropriate safety notifications to Health Authorities in accordance with applicable laws and regulations.

The Investigator must comply with any applicable site-specific requirements related to the reporting of SAEs (particularly deaths) involving study participants to the Independent Ethics Committee (IEC)/ Institutional Review Board (IRB) that approved the study.

In accordance with International Council for Harmonization Good Clinical Practice (ICH GCP), the Sponsor/designee will inform the Investigator of findings that could adversely affect the safety of participants, impact the conduct of the study or alter the IEC's/IRB's approval/favorable opinion to continue the study. In line with respective regulations, the Sponsor/designee will inform the Investigator of AEs that are both serious and unexpected and considered to be related to the administered product ("suspected unexpected serious adverse reactions" or SUSARs). The

Investigator should place copies of Safety Reports in the Investigator Site File. National regulations regarding Safety Report notifications to Investigators will be considered.

When specifically required by regulations and guidelines, the Sponsor/designee will provide appropriate Safety Reports directly to the concerned lead IEC/IRB and will maintain records of these notifications. When direct reporting is not clearly defined by national or site-specific regulations, the Investigator will be responsible for promptly notifying the concerned IEC/IRB of any Safety Reports provided by the Sponsor/designee and of filing copies of all related correspondence in the Investigator Site File.

For studies covered by the European Directive 2001/20/EC, the Sponsor's responsibilities regarding the reporting of SAEs/SUSARs/Safety Issues will be carried out in accordance with that Directive and with the related Detailed Guidance documents.

### 8.3.5 Pregnancy

Only pregnancies the Investigator considers to be related to the study intervention (e.g., resulting from a drug interaction with a contraceptive method) are AEs. However, all pregnancies with an estimated conception date during the period defined in Section 8.3.1 must be recorded in the AE page/section of the CRF for pregnancies in female partners of male participants. The Investigator must notify the Sponsor/designee in an expedited manner of any pregnancy using the Pregnancy Report Form, which must be transmitted by the same process specified for SAE reporting in [Appendix 4](#), section on Reporting Serious Adverse Events.

Investigators must actively follow up, document and report on the outcome of all these pregnancies, even if the participants are withdrawn from the study.

The Investigator must notify the Sponsor/designee of these outcomes using the Pregnancy Report Form. If an abnormal outcome occurs, the SAE Report Form will be used if the participant sustains an event and the Parent-Child/Fetus Adverse Event Report Form if the child/fetus sustains an event. Any abnormal outcome (e.g., spontaneous abortion, fetal death, stillbirth, congenital anomalies, ectopic pregnancy) must be reported in an expedited manner, as specified in Section 8.3.1, while normal outcomes must be reported within 45 days after delivery.

## 8.4 Treatment of Overdose

For this study, any dose of rac-PZQ greater than 1200 mg will be considered an overdose.

There have been no reports to date of acute intoxication caused by PZQ. Treatment is directed to symptoms as applicable.

Even if it not associated with an AE or a SAE, any overdose is recorded in the CRF and reported to drug safety in an expedited manner. Overdoses are reported on a SAE Report Form, following the procedure in [Appendix 4](#), section on Reporting Serious Adverse Events.

## 8.5 Pharmacokinetics

- Twenty-one venous blood samples of approximately 2 mL each collected in K3-EDTA tubes will be taken for measurement of plasma concentrations of R-(-)-PZQ and S-(+)-PZQ, as specified in the SoA in Section 1.3. Concentrations of both enantiomers will be added to calculate the rac-PZQ concentrations and these will be used to evaluate the PK parameters of the study intervention as primary objective. Plasma concentrations and PK parameters of the enantiomers will be evaluated as secondary endpoints.
- Samples will be taken per period with a catheter or by venipuncture for the measurement of drug's plasma concentration: Predose, 0.25, 0.5, 0.75, 1.0, 1.5, 2.0, 2.5, 3.0, 3.5, 4.0, 4.5, 5.0, 5.5, 6.0, 6.5, 7.0, 8.0, 9.0, 10.0 and 12.0 h following dosing. The quantification of R-(-)-PZQ and S-(+)-PZQ in K3-EDTA plasma will be performed using a validated assay method.
- The actual date and time (24-hour clock time) of each sample will be recorded to calculate actual time elapsed since the prior dose administration and recorded in the CRF.
- Except for the predose sample, all PK samples will be taken after dosing.
- The following noncompartmental PK parameters (Table 3) will be calculated from the individual plasma rac-PZQ, R-(-)-PZQ and S-(+)-PZQ concentration-time data obtained on Days 1, 8, 15 and 22 respectively, using commercial software Phoenix®/WinNonlin®, Version 6.3 or higher (Certara, L.P., Princeton, New Jersey), when appropriate. Cmax and AUC0-t are the main parameters for further statistical analysis.

**Table 3 Pharmacokinetic Parameters Derived from rac-PZQ Concentrations**

C max	Maximum observed drug concentration.
t max	Time of the maximum drug concentration.
t lag	Time prior to the first measurable (non-zero) concentration; calculated as last time point at which the concentration is <LLOQ before the occurrence of the first quantifiable concentration
λ z	Terminal rate constant.
t 1/2	Terminal elimination half-life.
AUC 0-t	Area under the drug concentration-time curve from time zero to the time of last measurable concentration using the linear-log trapezoidal method (linear up log down).
AUC 0-∞	Area under the drug concentration-time curve from time zero extrapolated to infinity.
%AUC extra	Percentage of AUC 0-∞ obtained by extrapolation
CL f	Apparent clearance
V Zf	Apparent volume of distribution during terminal phase

- Remaining samples collected for analyses of rac-PZQ concentrations may also be used to evaluate safety or efficacy aspects related to concerns arising during or after the study.
- The bioanalytical assessment will be outsourced to Nuvisan under the responsibility of Merck. PK parameter estimation and generation of PK TLFs will also be outsourced to Nuvisan.
- Primary and back up samples will be shipped separately. It is planned that pooled samples for concentration range estimation and enantiomer detection as well as metabolite identification will be prepared according to CRO's SOPs. These specificity samples originate from some of the blood samples collected for drug assays and may be used by the analytical laboratory to

determine suitable quantification ranges, enantiomer identification and exploratory metabolite identification.

- Details on processes for collection and shipment of these samples are in the Laboratory Manual. Retention time and possible analyses of samples after the end of study are specified in the respective ICF.

## 8.6 Pharmacodynamics

Not applicable.

## 8.7 Pharmacogenetics

Not applicable.

## 8.8 Biomarkers

Not applicable.

## 8.9 Immunogenicity Assessments

Not applicable.

### 9.3 Populations for Analyses

The analysis populations are specified below. The final decision to exclude participants from any analysis population will be made during a data review meeting prior to database lock without the information of treatment allocation.

Analysis Set	Description
Screening (SCR)	All participants, who provided informed consent, regardless of the participant's randomization and study intervention status in the study.
Safety (SAF)	All participants, who were administered any dose of any study intervention. Analyses will consider participants as treated.
PK	
All participants, who receive at least one dose of study intervention, have no clinically important protocol deviations or important events affecting PK, and provide at least one measurable postdose concentration. Participants will be analyzed per the actual study intervention they received.
 
The PK population will include all participants:
 

• Who have completed at least one study period without any relevant protocol deviations and factors likely to affect the comparability of PK results

• With adequate study intervention compliance

• With evaluable PK data, i.e., nonmissing values for primary endpoints in each study period.

 
If participants received prohibited concomitant therapy or medicines, as specified in Section 6.5, they will be excluded from the PK population. Relevant decisions will be made before database lock. All PK analyses will be based on this analysis set.

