### 7.2 Participant Discontinuation/Withdrawal from the Study

- A participant may withdraw from the study at any time, at his own request or may be withdrawn at any time at the discretion of the Investigator for safety, behavioral, compliance, or administrative reasons.
- At the time of discontinuing from the study, if possible, a discontinuation visit will be conducted, as listed in the SoA. The SoA specifies the data to collect at study discontinuation and follow-up, and any additional evaluations that need to be completed.
- If the participant withdraws consent for future involvement in the study, any data collected up to that point may still be used, but no future data can be generated, and any biological samples collected will be destroyed.
- A participant has the right at any time to request destruction of any biological samples taken. The investigator must document this in the site study records.
- The participant may be withdrawn by the Investigator due to participation in another clinical study.

- Vomiting within the first 6 hours after study drug administration, as vomiting interferes with the PK assessments in this study.
- Not consuming the whole breakfast before drug administration.

In case of premature withdrawal from the study, the investigations scheduled for the last visit (End of Treatment/ Safety Follow-up Visit) should be performed as soon as possible, but at least 7 days after last dosing. In any case, the appropriate section in the CRF must be completed.

The WHO guideline regarding drop-outs states the following: “Sponsors should select a sufficient number of study participants to allow for possible drop-outs or withdrawals. Because replacement of participants during the study could complicate the statistical model and analysis, drop-outs generally should not be replaced.”

After discussion with the contract research organization (CRO), the nonevaluable rate (including drop-out) was set at 10%. Therefore, the number of participants to be included in the study is set to 36 to cover a minimum of 32 evaluable participants (see Section 9.2). If 5 or more participants drop out of the study before completing period 4, additional participants may be randomized to meet the required minimal number of evaluable participants (N = 32).

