6.2 Final Analysis

The final, planned analyses identified in the CSP and in this IAP will be performed after the last participant has completed the last visit, i.e. end of treatment/safety follow-up visit with all trial data in-house, all data queries resolved, and the database locked.

A data review meeting will be held prior to database lock for the final analysis. In addition, no database can be locked until this IAP has been approved.

7 Changes to the Planned Analyses in the Clinical Study Protocol

There are no changes to the planned analyses in the CSP.

8 Protocol Deviations and Analysis Sets

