8.1 Definition of Protocol Deviations and Analysis Sets

Important protocol deviations are protocol deviations that might significantly affect the completeness, accuracy, and/or reliability of the study data or that might significantly affect a participant's rights, safety, or well-being.

The following deviations will be identified and confirmed prior to or at the Data Review Meeting at the latest.

Important protocol deviations include

- Deviations from the inclusion and exclusion criteria
- Concomitant medication violations (see Section 6.5.2 of the protocol)
- Use of prohibited medicines (see Section 6.5.3 of the protocol)
- Participants who receive incorrect treatment or dose
- Sample processing errors that may lead to inaccurate bioanalytical results
- Vomiting or diarrhea following oral dosing (these instances will be discussed on a case-by-case basis)
- Deviation from Good Clinical Practice

- Non-compliance to study procedures or deviations from study procedures likely to affect the primary endpoints (e.g. participant develops withdrawal criteria whilst in the study but is not withdrawn)
- Deviation from study medication compliance in terms of medical conditions and/or AEs that may have interfered with drug disposition or with respect to factors likely to affect the primary endpoints

All important protocol deviations will be documented in Clinical Data Interchange Standard Consortium (CDISC) Study Data Tabulation Model (SDTM) datasets whether identified through sites monitoring or medical review.

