8.2 Definition of Analysis Sets

Analysis Set	Description
Screening (SCR)	The Screening Analysis Set will include all participants, who provided informed consent, regardless of the participant’s randomization and study intervention status in the study.
Safety (SAF)	The Safety Analysis Set will include all participants who were administered any dose of any study intervention. Analyses will consider participants as treated. All safety analyses will be based on this analysis set.
PK	
The PK Analysis Set will include all participants, who receive at least one dose of study intervention, have no clinically important protocol deviations or important events affecting PK, and provide at least one measurable postdose concentration. Participants will be analyzed per the actual study intervention they received.
 
The PK population will include all participants:
 
 • Who have completed at least one study period without any relevant protocol deviations and factors likely to affect the comparability of PK results • With adequate study intervention compliance • With evaluable PK data, i.e., nonmissing values for primary endpoints in each completed study period. 
If participants received prohibited concomitant therapy or medicines, as specified in Section 6.5 of the CSP, they will be excluded from the PK population. Relevant decisions will be made before database lock. All PK analyses will be based on this analysis.

9 General Specifications for Data Analyses

Statistical analyses will be performed using the computer program package SAS[®] System for Windows[™] (Version 9.4 or later; SAS Institute, Cary, North Carolina, USA).

The results of this trial will be reported using summary tables, figures, and data listings, as appropriate. All data will be summarized by treatment sequence, period, treatment and/or scheduled time point, as appropriate. All individual data will be listed as measured in the individual participant data listing. Repeated and unscheduled measurements will be included in the listings.

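### Protocol 9.3 and SAP 8.2 do not settle whether one PK-affected or nonevaluable period removes the participant or only that period from the PK analysis set

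*Protocol*

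**What the plan says.** Protocol 9.3 and SAP 8.2 share most of the definition of the PK set.

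- **Lead sentence (both documents).** Dosed participants qualify if they "have no clinically important protocol deviations or important events affecting PK, and provide at least one measurable postdose concentration". This is a test on the participant.
- **First bullet (both documents).** The population takes in participants "Who have completed at least one study period without any relevant protocol deviations" or other factors that would disturb the PK comparison. This is a test on a period.
- **Third bullet (differs).** Protocol: "With evaluable PK data, i.e., nonmissing values for primary endpoints in each study period". SAP: "With evaluable PK data, i.e., nonmissing values for primary endpoints in each completed study period".
- **Prohibited medicines (both documents).** The whole participant is excluded. This is settled and not in dispute.

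SAP section 7 states: "There are no changes to the planned analyses in the CSP".

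Protocol 9.4.3 and SAP 16.1.1 have their own entry rules. The ANOVA needs one usable value on each product, and the CVwR model needs both reference values. Protocol 9.3 places exclusion decisions at a data review meeting before lock, without treatment allocation.

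On vomiting, Protocol 7.2 lists an episode within 6 hours of dosing among the withdrawal reasons, "as vomiting interferes with the PK assessments in this study". Protocol 5.2 lists the same event as an exclusion criterion. SAP 8.1 lists among important deviations "Vomiting or diarrhea following oral dosing (these instances will be discussed on a case-by-case basis".

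**The concern.** Take a participant with three clean periods and an event in the fourth that the data review judges to affect PK. The lead sentence removes the participant and all three clean profiles; the first bullet keeps the participant. The data review can decide whether the event affected PK, but no written rule tells it what to remove.

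The case is foreseeable, since Protocol Table 2 lists vomiting as very common.

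The third bullet raises two further issues. The added word in the SAP decides whether a participant who drops out after a clean period 2 or 3 is analysed, and it is not declared as a change. In either wording, one completed period without a primary endpoint discards valid profiles that the ANOVA entry rule would accept.

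At stake are the primary bioequivalence test and the CVwR that sets the widened limits, because both use this set.

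**Working it through.** **1. The plan's own figure.** Protocol 7.2 gives the planning rate in percent: "the nonevaluable rate (including drop-out) was set at 10". 32 / (1 − 0.10) = 35.6, rounded up to 36, which matches the planned number. 36 × 0.10 = 3.6, so about 4 participants. The power calculation is not in the public text and cannot be reproduced.

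**2. The rules applied to four cases.**

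| Case | Lead sentence | Bullet 1 | Bullet 3, Protocol | Bullet 3, SAP | ANOVA entry rule |
|---|---|---|---|---|---|
| A. Periods 1-3 clean, PK-affecting event in period 4 | out | in | depends on period 4 values | depends on period 4 values, if completed | accepts |
| B. Periods 1-2 clean, PK-affecting event in period 3, withdrawn | out | in | out | can be met | accepts |
| C. Drop-out after a clean period 2 or 3 | in | in | out | in | accepts |
| D. Four periods completed, no deviation, one period without a primary endpoint | in | in | out | out | accepts |

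A and B are unsettled. C turns on the added word. D is determinate but loses three valid profiles. In both sequences periods 1 and 2 supply one T and one R value, so the ANOVA rule accepts all four cases. Of the 2⁴ = 16 clean/affected patterns, 1 has all periods clean and (2² − 1) × (2² − 1) = 9 have at least one clean T and one clean R.

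**3. Precision.** Inputs: reference within-subject CVs of 33.4% (AUC) and 47.08% (Cmax) from Protocol 4.2.2, assumed equal for T and R. s = √ln(1 + CV²) gives 0.325 and 0.447. Log-scale half-width = t(0.95, df) × s / √n_eff, with df = profiles − participants − 4. In the fixed-effects model a four-period participant counts as 1 in n_eff, and one with only periods 1-3 counts as 2/3. The documents give no rate for case A, so 1, 2 or 4 of 36 are assumed.

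| Affected | Clean profiles at stake (of 144) | Profiles, excluded / kept | df | n_eff | Half-width AUC | Half-width Cmax | CI narrower if kept |
|---|---|---|---|---|---|---|---|
| 1 | 3 (2.1%) | 140 / 143 | 101 / 103 | 35 / 35.67 | 0.0913 / 0.0904 | 0.1256 / 0.1244 | 1.0% |
| 2 | 6 (4.2%) | 136 / 142 | 98 / 102 | 34 / 35.33 | 0.0926 / 0.0908 | 0.1274 / 0.1249 | 1.9% |
| 4 | 12 (8.3%) | 128 / 140 | 92 / 100 | 32 / 34.67 | 0.0955 / 0.0917 | 0.1314 / 0.1262 | 4.0% |

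Example, AUC with 4 affected: excluded 1.6616 × 0.325 / √32 = 0.0955; kept 1.6602 × 0.325 / √34.67 = 0.0917; the ratio is 0.960.

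**4. Power.** The plan's decision rule was simulated with both readings applied to the same trials: Method A ANOVA, 90% CI, limits from CVwR with k = 0.760 and the 69.84-143.19% cap, and GMR within 80-125%. There were at least 100,000 trials per cell, with Monte Carlo error at most 0.13 points. True GMRs of 0.90 and 0.95 are assumptions.

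| Affected | AUC, 0.90 | AUC, 0.95 | Cmax, 0.90 | Cmax, 0.95 |
|---|---|---|---|---|
| 1, excluded / kept | 81.2 / 81.8% | 96.6 / 96.8% | 88.7 / 89.2% | 96.8 / 97.1% |
| 2, excluded / kept | 80.7 / 82.0% | 96.3 / 96.8% | 87.8 / 88.8% | 96.5 / 97.0% |
| 4, excluded / kept | 78.4 / 80.9% | 95.3 / 96.5% | 86.2 / 88.3% | 95.6 / 96.7% |

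The gain runs from 0.2 to 2.5 points. If the event falls in period 3 instead, with 4 affected and two clean periods each, the CI is 3.0% narrower and the gain is 0.8 to 1.8 points.

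**The case against.** The best defence reads the bullets as the working form of a general lead sentence. Other SAP text supports that. Section 9 includes a participant who withdraws up to the time of discontinuation. Section 10.2.2 lists reasons for excluding individual concentrations. Section 16.1 flags invalid data separately from participants outside the set. Section 16.1.1 flags excluded parameters and asks only for one valid value on each product. All of this presupposes partial data from retained participants.

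The added word is likewise best read as a clarification. A literal four-period rule would leave the protocol's own first bullet and its ANOVA entry rule with almost nothing to do. Protocol 9.4 also defers analysis detail to the integrated analysis plan. Finally, exclusions are decided before lock without treatment allocation.

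Most of this stands. A reader might infer a flat contradiction with no preferred reading, or a completer analysis quietly replaced by the SAP; the documents support neither. But none of these sections overrides the set definition, and SAP 8.2 and 16.1 base all PK analyses on that set. The opposite reading, with lead sentence and bullets cumulative, is also coherent: it excludes the participant and leaves the first bullet almost idle. The data review applies a rule but does not supply one.

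**Conclusion.** The concern holds as a drafting fault in the primary population, with modest consequences. For cases A and B the text does not say whether the participant or the period goes, although period-level exclusion is the better-supported reading. For case D the rule is clear but discards usable data. For case C the SAP wording probably governs, and the fault is that it is not listed.

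The size is a CI about 1 to 4% narrower and about 0.2 to 2.5 points more power if clean periods are kept. This assumes 1 to 4 affected participants, events in period 4, equal T and R variance, and a GMR of 0.90 to 0.95. Four is not an upper limit: 10% is a planning assumption, and Protocol 7.2 itself provides for 5 or more drop-outs. Treatment-blind review limits bias.

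A reader might take the share of simulated trials in which the two readings give different bioequivalence verdicts as the harm. With 4 affected at GMR 0.90 that share is 6.7% for AUC. It counts switches both ways: about 2.0 of those points are trials that pass with exclusion and fail when the data are kept. The net effect is the power difference above.

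**What to change.** Change SAP 8.2 before database lock:

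- State that a PK-affecting deviation or event, or a nonevaluable primary endpoint, removes that period's values and not the participant.
- Replace the participant-level deviation clause in the lead sentence, and the third bullet's condition on every (completed) period, with a requirement of at least one valid period.
- Let the existing entry rules govern: one valid T and one valid R value for the ANOVA, both R values for CVwR.
- Keep the whole-participant exclusion for prohibited medicines.
- List the change in SAP section 7, and align Protocol 9.3 if the protocol is amended.

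Judging validity by parameter, so that a usable Cmax survives a failed AUC0-t and vice versa, is optional. Which events count as PK-affecting stays with the data review. The vomiting statements in Protocol 5.2, Protocol 7.2 and SAP 8.1 should be reconciled.

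The cost is wording only. No new data are needed, and the fixed-effects model already accepts unbalanced data. A formal protocol amendment would also need IRB/IEC approval under Protocol Appendix 2.
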